#### *Parallel Part*

[figure not shown]
If no stopping criteria have been met during the sequential part and if the IDMC issues a positive recommendation after each safety cohort and the Sponsor decides to proceed, the remaining 144 subjects (i.e., Cohort 4) will be randomly assigned in a 1:1:1:1 ratio to one of following treatment groups, yielding an overall randomization ratio of 3:1 active to placebo.

- ALX-0171 dose 1
- ALX-0171 dose 2
- ALX-0171 dose 3
- Placebo

In the event one or two dose groups are discontinued for safety, the remaining groups will enroll the number of subjects initially specified (i.e., 45 per arm).

The Placebo group will serve as comparator group for the 3 ALX-0171 dose groups. To achieve double-blinding across the different groups, each dose will be administered as two serial nebulizations. These two nebulizations will consist either of two nebulizations of ALX-0171, or one of ALX-0171 and one of placebo, or two nebulizations of placebo depending on the assigned treatment group (also see section 3.3.7).

An overview of the study flow is provided in [Figure 4](#).

**Figure 4: Overview of study flow**

Subjects will be screened as soon as possible after arrival to the hospital/emergency unit. After completion of the screening assessments and confirmation of subject's eligibility, randomization should follow as soon as possible but not more than 24 hours after arrival. Study drug administration should start as soon as possible after randomization with a maximum time interval of 3 hours following randomization. Subsequent doses of study drug will be administered at 24-hour intervals ( $\pm 4$  hours) relative to the first dose. No premedication is required or recommended per protocol, but an inhaled  $\beta 2$ -agonist may be administered at the discretion of the treating Investigator.

On the first 2 dosing days, inpatient hospital stay is required. Provided that the clinical response criteria have been met (which are based on adequate oral feeding and oxygen saturation), discharge from the hospital can take place per protocol at the Investigator's discretion from dosing Day 2 onwards after all required assessments of the 5 hours ( $\pm 1$  hour) post-dose time point have been completed. Subjects discharged after the second dose must return to the hospital for the third study drug administration (to be administered  $48 \pm 4$  hours after the first dose by the appropriately trained study personnel), and be monitored for a 2-hour pre-dose and post-dose period. Subjects who are not discharged

from the hospital after completion or premature discontinuation of study drug enter an in-hospital post-treatment period with assessments in the morning and evening. A Follow-Up (FU) visit is scheduled on Day 14 ( $\pm$  2 days), and an End of Study (EOS) visit on Day 28 ( $\pm$  2 days). For subjects prematurely withdrawn from the study, a Withdrawal visit is to be performed on the day of withdrawal.

The primary endpoint in this study is the evaluation of viral load in samples obtained via nasal mid-turbinate swabs. In particular, the time needed for the viral load (as assessed by plaque assay) to drop below the quantification limit (BQL) is calculated (time-to-BQL).

Secondary endpoints include:

- Safety will be assessed through AE collection, measurements of vital signs, peripheral capillary oxygen saturation (SpO2), physical examination and laboratory parameters. Safety lab assessments are planned two times during the study (at screening and at the FU visit) and will be performed by the local laboratory in order to allow timely availability of the results. Furthermore, an IDMC will be involved in the regular review of the available safety data.
- Clinical activity of ALX-0171: assessed through evaluation of clinical symptoms over time (SpO2, feeding, respiratory rate, wheezing, cough, respiratory muscle retractions, and general appearance) and further calculation of composite clinical scores such as Global Severity Score, Respiratory Assessment Change Score (RACS) and Respiratory Distress Assessment Instrument (RDAI).
- Time to clinical response, utilizing the criteria of adequate oxygen saturation and oral feeding (see below).

Subjects will be considered to have met the Clinical Response criteria when both of the following criteria are fulfilled:

- Stable oxygen saturation on room air, defined as SpO2 > 92% over a period of  $\geq$  4 hours. In case of oxygen supplementation, the level of supplementation is to be considered for reduction at least three times per day. Provided oxygen saturation is stable, attempts to remove the supplementation will be done at least three times a day.
- Adequate oral feeding which is sufficient to maintain sufficient hydration, in the judgment of the Investigator.

In addition, data on medical interventions will be captured in order to assess the impact of ALX-0171 on duration of hospitalization and the need for ventilation or transfer to an intensive care unit (ICU) setting.

Parent(s)/Caregiver(s) assessment of the clinical condition of the child will be done by daily completion of a diary during the hospital stay and up to the EOS (Day 28) visit. This diary includes scoring of respiratory symptoms over the past 24 hours (cough, wheezing, trouble breathing), evaluating the general health of the child by making a mark on a Visual

Analogue Scale (VAS) to indicate the child's health, and answering a question whether the child has returned to his/her normal condition from before the onset the RSV infection. For the period after discharge from the hospital, this diary will also allow to capture data on health care utilization and use of medication for respiratory symptoms.

The study will also evaluate pharmacokinetics, pharmacodynamics and immunogenicity:

- The systemic concentration of ALX-0171 will be evaluated in serum, as a surrogate for evaluating local (lung) concentration. A subset (48 subjects, i.e., 12 subjects per dose group) will undergo more extensive PK sample analysis (3 blood samples for PK assessment). The extensive sampling scheme might become mandatory during the study in order to achieve the predefined sample size. Replacement of subjects who are part of the extensive PK sampling will be done for those for whom not all 3 PK samples could be collected successfully and/or who have not completed study drug administration on dosing Day 1 or dosing Day 2. Subjects part of the extensive PK sampling who have not successfully received study drug on Day 1 or Day 2 do not need to undergo the full PK sampling schedule. In the remainder of subjects, only 1 PK blood sample will be taken. The number of subjects undergoing the more extensive PK sample analysis was determined to obtain sufficient precision on the PK parameters as described by Wang et al. [10].
- In addition, PD biomarker (Krebs von den Lungen [KL-6]) will be assessed (serum).
- Potential immunogenicity will also be assessed systemically (serum).

For determination of sample size, please refer to section 3.1.2.

#### *Estimated Study Duration*

The overall study duration is expected to be around 23 months. The planned study duration for each subject is approximately 28 days.

The completion of the study is defined as the last visit of the last subject (LSLV) participating in the study.

#### *Independent Data Monitoring Committee*

In line with applicable guidelines, an IDMC is assigned to monitor the study. The IDMC consists of an independent group of clinical experts not participating in the study and an independent statistician.

After each safety cohort (when the last subject in a safety cohort has completed treatment period), recruitment will be paused while the IDMC reviews the available cumulative safety data (i.e., all data from prior visits that have been done for all included subjects, including preceding cohorts).

After this comprehensive review of safety data, the IDMC will advise the Sponsor on proceeding to the subsequent cohort (i.e., the higher dose) and which planned dose levels

can be taken forward into the parallel part. This recommendation will complement the above-described predefined stopping criteria.

During the parallel part of the study, an IDMC review is planned after 72 subjects completed treatment.

Throughout the study, SAE information will be communicated in real time according to the reporting requirements. An ad-hoc meeting can be requested by the IDMC members.

The composition, objectives, and roles and responsibilities of the IDMC will be described in an IDMC charter, agreed with the IDMC members and Sponsor. The IDMC charter will also define and document the content of the safety summaries, and general procedures (including communications). The first version of the charter will be available prior to the initiation of the study.

### **3.1.2. STUDY RATIONALE AND DISCUSSION OF STUDY DESIGN**

Safety and tolerability of ALX-0171 have been evaluated in 3 Phase 1 studies in adults, and in a Phase 1/2a study in infants and young children hospitalized for RSV LRTI. Study ALX0171-C201 will include a similar population and aims primarily to evaluate the anti-viral effect of three doses of inhaled ALX-0171, as well as to assess the safety and clinical activity (see section 3.3.2 for dose selection rationale). The outcome of this dose ranging study will support the selection of the optimal dose and the most relevant endpoints for further clinical development.

Study ALX0171-C201 will start with a stepwise assessment of cohorts of 12 subjects, each being randomized in a 3:1 ratio to increasing doses of ALX-0171 or placebo (i.e., 9 subjects receiving ALX-0171 and 3 receiving placebo in each cohort). To guide dose escalation, stopping criteria have been included in the protocol (section 3.1.1). In addition, after each of these 3 sequential cohorts, recruitment will be paused in order to allow the IDMC to evaluate available cumulative safety data and recommend whether the subsequent cohort can be initiated and which planned dose levels can be taken forward into the parallel part. When these initial cohorts have been completed and safety has been confirmed, the study will continue with a parallel allocation to ALX-0171 or placebo. 144 eligible subjects will be randomly assigned in a 1:1:1:1 ratio to 1 of the 4 treatment groups (3 active groups and 1 placebo group).

The design of Study ALX0171-C201 allows an approach with a placebo-controlled group as representative comparison for the three active dose levels. The total volume and corresponding inhalation times of study drug per weight category is similar in all dosing groups, by using a combination of placebo and ALX-0171 (if applicable), administered via

2 serial nebulizations. This ensures blinding across the treatment groups (also see section 3.3.7).

The primary objective of the study is evaluation of the anti-viral effect of ALX-0171 compared to placebo.

As pharmacologically active doses will be used, clinical activity of ALX-0171 will be evaluated in order to assess if the pharmacological effect translates in clinical benefit to the subject. Other objectives include evaluation of pharmacokinetics, pharmacodynamics (biomarker), and immunogenicity.

Viral load will be assessed in samples obtained via nasal swabs collecting a mid-turbinate specimen. Based on the results of Study ALX0171-C104, the anti-viral effect of ALX-0171 will be mainly determined by the time to drop BQL in plaque cultures, which is the parameter that best reflects the inhibition of viral replication. Quantification of viral load by RT-qPCR will also be assessed as it is a more sensitive method than culture assay and has a good dynamic range. However, as the mode of action of ALX-0171 is to inhibit viral entry into the target cell, modest effects of ALX-0171 treatment on viral RNA are expected as complete viral particles that are unable to replicate, partially assembled virions, and whole and fragmented viral genome will be quantified by RT-qPCR in addition to fully replication-competent virus.

The clinical impact of treatment by ALX-0171 in infants and young children will be evaluated by changes in clinical symptoms and subsequent calculation of composite scores, the time needed to enable adequate feeding and oxygen saturation, need for medical interventions and length of hospital stay. Based on the clinical activity parameters measured during the study, composite scores that reflect the clinical status of the subject suffering from RSV will be calculated, including the Global Severity Score, RDAI score, and RACS. The Global Severity Score is based on a recent clinical score that allows categorisation of infants with respiratory infections on 7 different parameters: feeding intolerance, medical intervention, respiratory difficulty, respiratory frequency, apnea, general condition and fever [11, 12]. It takes into account all clinically relevant aspects of an RSV infected subject. The RDAI is a scoring system based on the presence and severity of wheezing and respiratory muscle retractions. The RACS is based on the RDAI and adds a standardized score for the change in respiratory rate.

Given the importance of timing of the administration of this anti-viral compound in the time course of the RSV infection, details on the time elapsed between onset of first clinical symptoms and start of treatment with study drug will be collected and analyzed. The need for medical interventions will be documented through collection of data on the need for and level of oxygen supplementation or respiratory support, need for transfer to ICU, duration of stay in ICU and overall hospital stay.

In addition to the assessments performed by healthcare professionals, the study will also collect information on how parents or caregivers perceive the clinical condition of the child through daily completion of a diary. This diary includes scoring of respiratory symptoms over the past 24 hours (cough, wheezing, trouble breathing), evaluating the general health of the child by making a mark on a VAS, and answering to a question if the child has returned to his/her normal condition from before the onset the RSV infection. For the period after discharge from the hospital, this diary will also capture data on health care utilization and use of medication for respiratory symptoms. The diary will be completed during hospital stay and daily thereafter up to the EOS (Day 28) visit as RSV induced bronchiolitis is often associated with continuing respiratory symptoms following hospitalization.

The systemic concentration of ALX-0171 will be evaluated in serum, as a surrogate for local (lung) concentrations. Potential immunogenicity will also be assessed systemically (serum), both pre-dose and post-dose (14 days post initial drug administration) and results will be correlated with PK, PD and safety findings.

Systemic levels of the serum biomarker KL-6 will be determined in left-over serum samples. Serum KL-6 was shown to indicate disease activity in various interstitial lung diseases and is believed to reflect the presence of alveolar damage [13, 14]. High serum KL-6 levels in RSV-infected infants correlate with low SpO2 and need for O2 administration [15]. These findings suggest that serum KL-6 is associated with the severity of RSV bronchiolitis, and that it may provide additional insight on potential treatment benefits.

The intended volume of blood to be withdrawn for each of the assessments is based on the minimum required volume for each of the respective analyses, and is in line with the volumes allowed per applicable guidelines [16-20].

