### 3.2.1. INCLUSION CRITERIA

A subject will be eligible for study participation if he/she meets all of the following criteria at screening and randomization, unless specified otherwise:

1. Subject is a male or female infant or young child aged 28 days to <2 years with gestational age  $\geq$  33 weeks at screening.
2. Subject weighs between  $\geq$  3.0 kg and < 15.0 kg at screening.
3. Subject is otherwise healthy, but is hospitalized for and clinically diagnosed with RSV LRTI (bronchiolitis or broncho-pneumonia), i.e., showing typical clinical signs and symptoms such as tachypnea, wheezing, cough, crackles, use of accessory muscles and/or nasal flaring.
4. Subject has a positive RSV diagnostic test at screening.##
5. Subject is expected to have to stay in the hospital for at least 24 hours (according to the Investigator's judgment at screening).
6. Symptoms likely related to RSV infection (i.e., the symptoms present need to be probably linked to the current RSV infection according to Investigator's judgment) have appeared within 4 days of screening and are not yet improving at screening and randomization.
7. Subject fulfils at least two of the following RSV disease severity criteria at screening and randomization:
  - Inadequate oral feeding that requires feeding support (i.e., nasogastric tube or i.v. line)
  - Inadequate oxygen saturation defined as:
    - Oxygen saturation ( $SpO_2$ )  $\leq$  92% on room air or
    - Requiring oxygen supplementation to maintain oxygen saturation  $>$  90% with documented pre-supplementation value  $\leq$  92%
  - Signs of respiratory distress defined as:
    - Respiratory rate  $\geq$  50 per minute in infants up to 12 months of age, and  $\geq$  40 per minute in children above 12 months and/ or
    - Moderate or marked respiratory muscle retractions

---

## RSV infection will be confirmed either according to routine site practice (PCR or diagnostic quick test), or using a (Sponsor-provided) commercial kit.

8. Subject has normal psychomotor development.
9. Parent(s)/legal guardian(s) provide written informed consent in accordance with locally approved consent process at screening.
10. The parent(s)/legal guardian(s) are able and willing to comply with the study protocol procedures.

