#### Baseline disease characteristics:

- RSV diagnosis (test method, test result)
- RSV signs and symptoms
- Number of days between symptom onset and first dose of study drug
- RSV severity criteria :
  - Number of subjects with inadequate oral feeding,
  - Number of subjects with inadequate oxygen saturation,

- Number of subjects with respiratory distress,
  - Number of subjects with inadequate feeding and inadequate oxygen saturation,
  - Number of subjects with inadequate feeding, inadequate oxygen saturation and respiratory distress.
- 
- Global Severity Score (GSS)
  - RDAI score
  - Number of subjects on oxygen supplementation

A listing for above mentioned demographic parameters and another for these baseline characteristics related parameters will be produced for all subjects in the mITT population.

The 19 viral screening tests performed at Baseline (please refer to 19.4 Appendix D for the list of viruses/bacteria tested) and their result (positive or negative) will be tabulated together with general subgroup classification (RSV only or Co-Infected) and will also be listed individually.

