### 7.1 Primary Efficacy Endpoint Evaluation

The primary endpoint for this trial is the time needed for the viral load to drop below the plaque assay quantification limit (time-to-BQL) in nasal mid-turbinate swab specimens. Time to BQL is defined as the time from the reference point (first dosing) to the first occurrence of a value below the limit of quantification, provided the next measured value is below the limit as well. The time to event for subjects with missing data and/or who did not reach BQL during the trial will be censored at the last nonmissing viral load assessment .

The time-to-BQL will be compared between each of the ALX-0171 treatment groups and the combined placebo group using a log-rank test. The null hypothesis of this test assumes no difference in time-to-BQL between Placebo and ALX-0171 treated subjects. The tests will be performed in a sequential way to preserve the family-wise error rate at 0.05. Specifically, dose 3 (highest dose) of ALX-0171 will first be tested against the combined placebo group at the 0.05 significance level. Dose 2 of ALX-0171 will only be compared to placebo at the 0.05 significance level if the comparison of dose 3 with placebo is significant. Consequently, dose 1 of ALX-0171 will only be compared to placebo at the 0.05 significance level if the comparison of dose 2 of ALX-0171 with placebo is significant. The primary efficacy endpoint will be evaluated using the mITT population.

The logrank test is based on the assumptions that censoring is unrelated to prognosis and the event probabilities are the same for subjects recruited early and late in the study. Kaplan-Meier (KM) estimates on time-to-BQL will be tabulated (Median, 25th, 75th percentile with confidence interval and general information on censoring) and a graph of the Kaplan-Meier survival curve will be presented.

The data will also be analyzed using a Cox proportional hazards regression model with time to BQL as dependent variable, and treatment group, viral load at baseline and co-infected subject group as independent variables. The hazard ratio (HR) from the Cox model along with the 95% CI will be reported. This analysis will only be performed for the treatment groups where the comparison was significant as analyzed by the log rank test.

For sensitivity analyses, the primary endpoint will also be evaluated using:

- the RSV Infected population
- the Per Protocol population.

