#### 7.4 Subgroups Analysis

Subgroups analysis will be performed on the mITT population for the following subgroups:

- Age category: <6 months, 6 - <12 months and  $\geq$ 12 months
- Subjects with inadequate oral feeding and inadequate oxygen saturation at baseline vs other
- Co-infected subjects vs RSV only subjects

The analyses listed below will be performed on the subgroups mentioned above:

- Time to BQL based on the plaque assay summarized using Kaplan Meier estimates
- GSS, summarized using descriptive statistics of the actual values and the change from baseline over time
- Time to clinical response, summarized using Kaplan Meier estimates
- Time between first study drug administration and discharge, summarized using descriptives statistics and Kaplan Meier estimates

Subgroups analyses on subjects with inadequate feeding and inadequate oxygen saturation at baseline and co-infected subjects will be performed if at least 15% of the subjects have inadequate feeding and inadequate oxygen saturation at baseline, and are co-infected; respectively.

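### Time from symptom onset to first dose, which the protocol says will be analysed because antiviral timing matters, is only summarised at baseline in the SAP and enters no efficacy analysis

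*Protocol*

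**What the plan says.** Protocol 3.1.2 gives a reason, "Given the importance of timing of the administration of this anti-viral compound in the time course of the RSV infection", and then a commitment: "details on the time elapsed between onset of first clinical symptoms and start of treatment with study drug will be collected and analyzed". Protocol 3.6 (Statistics) names no specific analysis of this variable.

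Three rules set the range of illness days at treatment:
- Inclusion criterion 6 (Protocol 3.2.1) requires symptoms that "have appeared within 4 days of screening and are not yet improving at screening and randomization".
- Protocol 3.1.1, under the study-flow figure, says "randomization should follow as soon as possible but not more than 24 hours after arrival".
- The same text has dosing start "with a maximum time interval of 3 hours following randomization".

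In the SAP the variable appears as a baseline disease characteristic in 6.3, "Number of days between symptom onset and first dose of study drug". It is summarised for the mITT, RSV-infected and per-protocol populations (Table 14.1.2.2, flagged for topline) and listed (Listing 16.2.2.2). Section 14.1.5 gives the derivation and sets a missing onset time to midnight.

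It is absent from the efficacy analyses:
- The primary log-rank test in 7.1 names no strata or covariates. The Cox model there has "treatment group, viral load at baseline and co-infected subject group as independent variables", and is run only for dose groups whose log-rank comparison is significant.
- The GSS mixed model in 7.2.1 has baseline value, treatment, timepoint and their interaction.
- In 7.4, "Subgroups analysis will be performed on the mITT population for the following subgroups" is followed by age category, a baseline severity split and co-infection status.

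Protocol 3.3.3 describes randomisation that balances arms overall and within the PK substudy. Symptom duration is not named.

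**The concern.** RSV infection clears on its own and the primary endpoint is a short clearance time, so days since onset is a plausible predictor of both time-to-BQL and change in GSS. The protocol singles the variable out for that kind of reason. The three-day course is also justified as covering the interval before the infant's own immune response takes over, so position in the illness is part of the rationale.

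A baseline table by arm shows whether illness day is balanced. It cannot show whether the treatment effect changes with illness day, and it gives no estimate adjusted for an imbalance it reveals. If the result is null or mixed, there would be no prespecified analysis with which to look at late treatment. That matters in a trial meant to guide the choice of dose and endpoints for further development.

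**Working it through.** **Window from onset to first dose.** 4 days (inclusion 6) + 24 h (arrival to randomisation) + 3 h (randomisation to dose) = 4 + 1 + 0.125 = 5.125 days. This upper limit applies when screening coincides with arrival.

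**The plan's own power figure.** Inputs from Protocol 3.1.2: 45 per arm, medians of 1 day and 0.5 day, two-sided 0.05, 85% power, 15% drop-out. With exponential times the hazard ratio (HR) is 1/0.5 = 2. Schoenfeld events = 4(1.960 + 1.036)²/(ln 2)² = 75, or 38 per arm; 38/0.85 = 44.7, so 45 per arm. In the other direction, 0.85 × 90 = 76.5 events gives power Φ(√76.5 × ln 2/2 − 1.96) = 0.858. The stated 85% reproduces. The calculation has no term for symptom duration.

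**What leaving the variable out could cost in precision.** The documents give no prognostic effect for illness day, so this is an illustration only. Assumptions: 38 evaluable infants per arm, HR 2 among infants of the same illness day, onset-to-dose time uniform on 0 to 5 days, exponential event times observed exactly, no censoring, 4,000 simulated trials. The stratified test uses three equal bands of duration.

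| Clearance hazard per extra day of illness | Power, unstratified log-rank | Power, stratified log-rank |
|---|---|---|
| ×1.00 | 0.84 | 0.79 |
| ×1.11 | 0.82 | 0.80 |
| ×1.22 | 0.77 | 0.78 |
| ×1.35 | 0.73 | 0.78 |
| ×1.65 | 0.63 | 0.77 |

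Accounting for duration helps only if it is clearly prognostic, from about ×1.2 per day. If it is not prognostic, stratifying costs about 5 points of power. That favours leaving the primary test alone and adjusting in supportive models. The protocol states its effect as overall medians, so the table does not show that 85% is wrong. It shows what adjustment might gain or lose.

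**What a subgroup could show.** In half of one pairwise comparison, the 95% CI factor for the HR is exp(1.96 × 2/√events). With 45 events (every infant) it is exp(0.584) = 1.79. With 76.5/2 = 38.25 events (after 15% drop-out) it is exp(0.634) = 1.89. Power for HR 2 in that half is 0.57.

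For an interaction between halves, SE = √2 × 2/√38.25 = 0.457. For HR 2.5 v 1.6, ln(2.5/1.6) = 0.446, giving power 0.16. For HR 3 v 1.33, ln(3/1.33) = 0.813, giving power 0.43. These analyses can describe a pattern but cannot confirm one.

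**The case against.** The strongest reply is that nothing promised has been dropped. Protocol 3.1.2 commits to collecting and analysing the variable, not to a covariate, a subgroup or an interaction test, and Protocol 3.6 names none. The SAP derives it, tabulates it in three populations and lists it. In the narrowest sense that is analysis. This stands, so a reader should not infer a breach of protocol or an analysis that SAP section 13 ought to have declared as removed. It does not answer the stated reason for the commitment, which a baseline table cannot address.

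A reader might also infer that pooling illness days biases the primary comparison. It does not. Randomisation makes the arms comparable in expectation, and chance imbalance is already within the log-rank test's type I error.

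A third tempting step is to set a chance imbalance in illness day beside the 0.5-day effect. With an assumed SD of 1.0 to 1.5 days, 1.96 × SD × √(2/45) is 0.41 to 0.62 day, which looks as large as the effect. The two are different quantities: one is mean days since onset, the other median time to clearance. They correspond only if a day of illness shortens clearance by a day, and the documents give no such slope. At an illustrative ×1.22 per day the imbalance amounts to an HR of about 1.09 to 1.13 (1.22 to the power 0.41 and 0.62), against the planned HR of 2.

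Finally, eligibility already narrows illness stage, and baseline viral load in the Cox model and baseline GSS in the mixed model may absorb part of its effect. That is fair. But the Cox model is not run after a non-significant log-rank test, so a null primary result would have no adjusted analysis at all.

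**Conclusion.** The point holds as a gap between the protocol's stated interest and the SAP's efficacy analyses. The primary test needs no change. The cost is possibly some precision, no estimate adjusted for illness day if it is imbalanced by chance, and no prespecified view of whether the effect depends on timing across a window of up to about 5.1 days.

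The loss of precision cannot be sized from the documents. Under the illustration it runs from none to appreciable, depending on an unknown prognostic effect. The missing look at timing does not depend on that assumption. The remedy would support description only: interaction power was 0.16 to 0.43 in the cases checked, so it could not establish that a null result was due to late treatment. The change is worth making because the variable is already derived and the protocol itself calls timing important.

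**What to change.** - **SAP 7.1:** leave the log-rank test and its testing order unchanged. Add days from onset to first dose as a continuous covariate in the supportive Cox model. Run that model for all dose groups whatever the log-rank result, labelled supportive and outside the testing sequence.
- **SAP 7.2.1:** add the same continuous covariate to the GSS mixed model.
- **SAP 7.4:** add a descriptive, exploratory subgroup by days since onset, for example split at the median, to the four analyses already listed there.
- **SAP 13:** record these additions. If the sponsor prefers not to make them, state there that only a baseline summary of this variable is planned.

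The cost is SAP wording, changed model terms in the Cox and GSS tables, and one more part in each of Tables 14.2.8.1 to 14.2.8.4. Table 14.3.1.9 also gains a part, because SAP 8.1.8 carries the 7.4 subgroups into the adverse event tabulation. No new data are needed.

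There are two limits to state alongside. Subgroup estimates will be imprecise. Setting a missing onset time to midnight can lengthen the derived interval by up to nearly a day, so some infants near the cut will be misclassified; the continuous covariate avoids the cut but carries the same measurement error.
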